1 INTRODUCTION

There are estimated to be more than 140 million contact lens (CL) wearers throughout the world and approximately 50-75% of CL wearers report suffering from symptoms of irritation while wearing their lenses.¹ CL-related dryness is a leading cause of CL discontinuation^{1 2} and two factors reportedly related to CL dryness include a rapid pre-lens tear film thinning time and lenses with a higher nominal water content.³

Evaporimetry is a non-invasive method of assessing the rate of evaporation of the tear film from the front surface of the eye. At present, there is only one commercial evaporimeter, the Eye-VapoMeter (Delfin Technologies Ltd., Finland), available for clinical use. The 2017 TFOS DEWS II Tear Film report noted that there is currently a lack of reliable, commercially available evaporimeters. The report stressed that the development of evaporimeters that can be used in a clinical setting under a variety of temperatures and humidities would be extremely useful.⁴

The Eye-VapoMeter was initially designed as a dermatological device to measure the rate of skin evaporation. The device was modified by incorporating an eye cup from a swimming goggle onto the base of the instrument and was validated for ocular use in 2014.⁵

All other evaporimeters previously described in the literature have only been used within a research setting. To our knowledge, there has only been one previous evaporimeter which was capable of binocularly measuring the tear evaporation rate (TER). Tsubota and Yamada reported on the development of an evaporimeter capable of simultaneously measuring both eyes in 1992.⁶ The evaporimeter consisted of a modified swimming goggle which had a 44 ml closed cylinder attached to each side of the goggle. The cylinders were needed to accommodate the large size of the sensors, which were used to record the temperature and relative humidity.

To overcome various problems associated with the Eye-VapoMeter and the Yamada/Tsubota evaporimeter, a novel, prototype goggle-based evaporimeter has been designed to simultaneously measure TER from both eyes at the same time. The benefit of a simultaneous TER measurement is less chair time for both the patient and practitioner.

The prototype evaporimeter incorporates a small 2.5 x 2.5 mm² temperature and humidity sensor into each lens of a swimming goggle, which eliminates the need to alter the original design of the goggle. The sensors sample the humidity and temperature 4 times per second and are positioned closer to the eye than inside the Eye-VapoMeter or the Yamada/Tsubota evaporimeter. The location of the sensor can provide a more accurate measurement of the humidity at the ocular surface by reducing the amount of extraneous air volume within the goggle.

Due to the relative lack of previously published research investigating evaporimetry and CLs, the purpose of this pilot study is to compare the effect of DAILIES TOTAL1, a low water content silicone hydrogel lens, and Biotrue ONEday, a high water content hydrogel lens, on TER. The study will also serve to validate the novel, in-house developed evaporimeter.

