2 OBJECTIVES

The objective of the study is to compare the rate of tear evaporation, measured with a novel evaporimeter, before and after DAILIES TOTAL1 and Biotrue ONEday CLs are worn in symptomatic and asymptomatic contact lens wearers.

The primary outcome variable for this study are the slopes calculated from the change in relative humidity over time.

Other variables of interest include:

- Contact lens dry eye questionnaire-8 (CLDEQ-8) score
- Comfort (subjective rating)
- Dryness (subjective rating)
- Non-invasive break up time
- Lipid layer thickness (Tearscope, LipiView II)
- Ocular surface area (mm²)
- Volume inside the goggle (cm³)

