4 MATERIALS AND METHODS

4.1 STUDY DESIGN

4.1.1 OVERALL DESIGN

[figure not shown]
This study is a prospective, double-masked (investigator and participant), contralateral, non-dispensing study. Each participant will be randomized to wear DT1 in one eye and BOD in the fellow eye. Both lenses will be worn on a daily wear basis. This study will involve 3 scheduled visits over 2 days.

Visit 1: Screening and contact lens fitting visit

Visit 2: Baseline dispensing visit with BOD and DT1 lenses (morning visit)

Visit 3: Follow up visit with BOD and DT1 lenses (afternoon visit)

Visit 2 (baseline visit) and Visit 3 (follow up visit) will be conducted on the same day. There will be 5.5 hours \pm 30 minutes between Visit 2 and Visit 3, during which time participants are not required to remain at the School of Optometry & Vision Science.

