4.1.2 RANDOMIZATION

A randomization schedule will be generated using a web-based program: (www.randomization.com). Participants will be randomized to the type of contact lens to be worn in each eye at Visit 2. A separate randomization will be generated for symptomatic and asymptomatic participants. The final study randomization schedule will be generated by CORE's Database Administrator, and provided to the research assistants for the study. Study investigators will remain masked to the randomization schedule until the interim data analysis. Study investigators will be granted access to the randomization schedule for the first 10 symptomatic and 10 asymptomatic participants in order to conduct the interim data analysis. Following

calculation of the sample size required to complete the study, study investigators will remain masked to the remainder of the randomization schedule until the study is completed and the database is locked.

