4.5.16 EVAPORIMETRY

The participant will be seated at an adjustable height table and will place their elbows on the table. The participant will hold a pair of modified swimming goggles (Figures 1A and 1B) over their eyes for 20 seconds while their eyes are open. The participant will be prompted to blink every 3 seconds during the measurement using a metronome (<https://www.youtube.com/watch?v=9ypeNJJeKIs>). The goggle will be removed and ventilated in front of a fan until the relative humidity returns to

baseline levels. The goggle will then be placed over the eyes for 20 seconds while they are closed to measure the evaporation rate from the skin. Three consecutive measurements of open eye and closed eye measurements will be taken. Recordings of the temperature and relative humidity during the measurement will be saved as a text file and images of the temperature and humidity versus time plotted as a graph will be saved as a png file. The rate of tear evaporation will be calculated from slope derived from the change in relative humidity over time. The evaporation rate from the ocular surface will be calculated by subtracting the evaporation rate of closed eye from the evaporation rate of the open eye. The average of three ocular surface evaporation rates will be calculated for each eye.

[figure not shown]

Figure 1: (A) Evaporimeter with arrows showing the location of the temperature/humidity sensors in the swimming goggle. (B) View of the front of the evaporimeter.

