10 STATISTICAL ANALYSIS AND DATA MANAGEMENT

10.1 STATISTICAL ANALYSIS

All data will be analyzed by CORE at the University of Waterloo on unmasked data using Microsoft Excel and statistical analysis software such as GraphPad and SPSS. Interim data analysis will be conducted after 10 symptomatic and 10 asymptomatic participants have completed the study to determine the optimal time period over which to calculate the slope. The results of the interim data analysis will also be used to calculate the sample size.

Descriptive statistics will be provided on information regarding baseline variables (age, sex, contact lens refractive error distribution, etc.). Data may be evaluated for individual groups

(asymptomatic versus symptomatic) and when both groups are combined. Data will be tested for normality of distribution using Shapiro-Wilk tests. A p -value of < 0.05 will be considered statistically significant. Additional analysis may be conducted.

Table 4 lists the primary outcome variables and anticipated statistical procedures.

Table 4: Outcome variables and anticipated statistical procedures

| Variable | Analysis | Statistical test |
|--------------------------------------------------------------------------------------------------------------------------------------------------------------|--------------------------------------------------------------------------------------------------------------------|--------------------------------------------------------------------------------------------------------------------|
| Tear evaporation rate | Change in relative humidity over time | Slope |
| Tear evaporation rate/Time | Effect of lens type | RMANOVA Mauchly's test of sphericity Greenhouse-Geisser p values Tukey HSD post hoc Paired t -test |
| Tear evaporation rate/ Subjective ratings/Non- invasive breakup time/Lp d ayer thickness (Lp View II - continuous)/Area of the ocular surface | Relationship between tear evaporation rate and subjective comfort and dryness/other tear film assessments | Pearson correlation – r |
| Tear evaporation rate/ Lp d ayer thickness (Tearscope - ordinal)/ Volume of the goggle | Relationship between tear evaporation rate and lpdayer thickness | Spearman correlation – ρ |

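### Table 4 compares the lenses without the randomised eye side, so a stable right-left difference in sensor gain, goggle volume or seal would be counted as error in the DT1-BOD comparison and cost precision

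*Combined protocol and SAP*

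**What the plan says.** Section 1 describes a device "designed to simultaneously measure TER from both eyes at the same time", which "incorporates a small 2.5 x 2.5 mm² temperature and humidity sensor into each lens of a swimming goggle". That the right sensor always reads the right eye follows from this layout; it is not stated outright. The protocol describes no swapping, matching or cross-calibration of the sensors.

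On design, Section 4.1.1 says "Each participant will be randomized to wear DT1 in one eye and BOD in the fellow eye". Section 4.1.2 adds that "A separate randomization will be generated for symptomatic and asymptomatic participants", but gives no block size and does not say whether right and left are balanced.

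On the outcome, Section 2 says "The primary outcome variable for this study are the slopes calculated from the change in relative humidity over time". Section 4.5.16 has the ocular surface rate "calculated by subtracting the evaporation rate of closed eye from the evaporation rate of the open eye", averaged over three replicates for each eye.

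On analysis, the Table 4 row headed "Effect of lens type" lists RMANOVA with post hoc tests and a paired t-test. It names no eye, side, sensor or allocation term and no baseline adjustment. Goggle volume and ocular surface area appear in Table 4 only as correlates of evaporation rate.

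**The concern.** Within a participant, lens and side are completely confounded: if DT1 is on the right, the DT1-BOD difference is also a right-left difference. Any stable right-left difference therefore enters that participant's value with a plus or minus sign set by the allocation. The trial knows the sign, because it randomised it, but the planned tests ignore it and treat the resulting spread as noise.

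At stake is precision in a small paired study of an in-house device that the study itself is meant to validate. A real lens difference could be missed, and the interim SD that feeds the sample size calculation (Sections 4.2.1 and 10.1) would be too large. If the sides happen to be unevenly split, part of the side difference also moves the lens estimate.

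**Working it through.** **Which sensor differences survive.** Take an illustrative open-eye slope of 0.80 and closed-eye slope of 0.30, so the true net slope is 0.50.
- Constant humidity offset of 3 points: net slope 0.50. It cancels in the slope.
- Additive slope error of 0.1, equal in both readings: (0.80 + 0.1) - (0.30 + 0.1) = 0.50. It cancels in the subtraction.
- Gain error of 5% or 10%: 1.05 × 0.50 = 0.525, or 1.10 × 0.50 = 0.55. It survives. A stable side difference in goggle air volume acts in the same way. Averaging replicates does not remove either.

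**Model.** For participant i, D_i = DT1 - BOD = δ + x_i·b + e_i, where x_i = +1 if DT1 is in the right eye and -1 if in the left, b is the surviving right-left difference, and SD(e) = 1.

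**Inputs.** The documents state no N, power, effect size or SD for this comparison, so there is no figure of the plan to reproduce. From the documents: at least 10 + 10 completers (Section 4.2.2) and a significance level of 0.05 (Section 4.2.1). Assumed: two-sided testing; δ = 0.66 SD, which gives the paired t-test 80% power at n = 20 when b = 0; b = 0.25, 0.5 or 1.0 SD.

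**Variance.** Ignoring x gives Var(D) of about 1 + b² = 1.06, 1.25 and 2.0. A sample size based on that SD grows by the same factors.

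**Standard error at n = 20.**
- Balanced sides: the b terms cancel in the mean, so the true SE is √(1/20) = 0.224. The paired test reports about √[(1 + b²·20/19)/20] = 0.231, 0.251 and 0.320, which is too large.
- Simple randomisation: true and reported SE are both about √[(1 + b²)/20] = 0.230, 0.250 and 0.316. This is valid, but wider than necessary.

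**Simulation, n = 20** (40,000 trials per cell):

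| b (SD) | Paired power, balanced | Adjusted power, balanced | Paired type I error, balanced | Paired power, simple | Adjusted power, simple | Paired type I error, simple |
|---|---|---|---|---|---|---|
| 0 | 0.80 | 0.80 | 0.048 | 0.80 | 0.78 | 0.051 |
| 0.25 | 0.78 | 0.80 | 0.043 | 0.78 | 0.78 | 0.051 |
| 0.5 | 0.72 | 0.80 | 0.028 | 0.71 | 0.77 | 0.049 |
| 1.0 | 0.49 | 0.80 | 0.006 | 0.50 | 0.77 | 0.051 |

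The adjusted test holds type I error at 0.048 to 0.053 in every row.

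**Chance imbalance.** The paired mean shifts by mean(x)·b. For a 7:3 split in a group of 10, mean(x) = (7 - 3)/10 = 0.4; under simple randomisation a split at least that uneven has probability 352/1024 = 34%. For 13:7 in 20, mean(x) = 0.3, with probability 26% for that or worse. Given a 13:7 split, type I error is 5.6%, 6.6% and 7.7% for b = 0.25, 0.5 and 1.0.

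**Cost of adjusting when b = 0.** Balanced: 0.801 to 0.799 at n = 20, and 0.802 to 0.791 at n = 10 (δ = 0.996). Simple: 0.800 to 0.777 at n = 20, and 0.800 to 0.736 at n = 10.

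**The case against.** A reader might infer that any mismatch between the sensors contaminates the lens comparison, or that its error bars are wrong whatever the schedule. The documents support neither. The slope and the closed-eye subtraction remove two common kinds of sensor error. Randomising lens to eye prevents systematic bias. The error bars are too wide if sides are balanced and valid on average if they are not forced to balance; only an unlucky split raises type I error, and modestly.

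Four further points deserve weight.
- **The size of b is unknown.** At 0.25 SD the loss is only about 2 power points. Hand pressure that varies from person to person is ordinary noise, and no side term removes it. This stands.
- **The no-lens baseline could do the job.** Both eyes are measured without lenses twice at Visit 2 (Section 4.4.3), and Table 4 lists time alongside evaporation rate. A constant side difference would cancel in a change from baseline or a lens-by-time contrast. But Table 4 does not commit to either, and the lens hypothesis in Section 3 concerns the rate after at least 6 hours of wear.
- **A larger interim SD would raise the sample size and so restore power.** True, up to the ceiling of 50 participants. The cost then becomes participants rather than power.
- **This is a pilot with anticipated, not fixed, tests.** That limits the weight of the point, but also makes the change easy.

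**Conclusion.** The point holds as a cheap improvement in precision, not as a validity failure. A stable right-left difference that survives the slope and the subtraction is left in the error of the lens comparison, although the randomised allocation could remove it. Under the assumed range of 0.25 to 1.0 SD at n = 20, this costs from about 2 to about 30 power points, and a sample size based on the unadjusted SD would be 1.06 to 2.0 times what is needed.

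This rests on three assumptions: that each sensor always reads the same-side eye, which is inferred from the goggle layout; that the side difference is reasonably stable across participants; and that b falls in the range shown, for which the documents give no evidence. Whether the planned test is conservative or merely imprecise depends on the balance of the schedule, which Section 4.1.2 leaves open.

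**What to change.** 1. In Table 4, replace the paired t-test for lens type by a regression of the DT1-BOD difference on allocation coded +1/-1, and test the intercept. Fit it in the combined sample.
2. In the RMANOVA, enter allocation (which lens is in the right eye) as a between-person factor; the lens-by-allocation interaction then carries the side effect. Side cannot be crossed with lens as a second within-person factor, because each participant fills only two of the four lens-by-side cells.
3. Use the residual SD from the adjusted model for the interim sample size.
4. State in Section 4.1.2 whether the schedule balances right and left within each symptom group.
5. Report the mean right-left difference at the two no-lens Visit 2 sessions. It estimates b, needs no unmasking, and serves the validation aim.

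No new data are needed. The cost is one degree of freedom. If there is no side effect, the power loss is under 2 points with balanced sides; under simple randomisation it is about 2 points at n = 20 and 6 points at n = 10. In a single group of 10 under simple randomisation, adjustment is still the worse choice at b = 0.25 SD (0.740 against 0.780), which is why it belongs in the combined sample.

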4.4.3 VISIT 2: BASELINE AND DISPENSING VISIT

- Participants will attend the visit having been awake for at least 2 hours.
- Participants will not have worn any contact lenses, used any eye drops or artificial tears, or worn any eye makeup on the day of the visit. Participants who have worn lenses, used eye drops, used artificial tears, or worn eye makeup on the day of the visit will be rescheduled.
- Monocular and binocular logMAR visual acuity will be recorded with high contrast letters under high illumination with spectacles or spectacle refraction.
- Slit lamp biomicroscopy using white light.

The participant will be assigned a randomization ID in order to determine which type of CL will be inserted into each eye.

Participants will be required to adapt to the room environment for at least 15 minutes prior to reporting subjective monocular ratings and performing baseline evaporimetry measurements. The

participant will apply thin layer of petroleum jelly will be applied to the skin surrounding the eye using a cotton tipped applicator to minimize the amount of evaporation from the skin.

- The participant will be asked to give subjective monocular ratings for:
 - Comfort
 - Dryness
 - Burning or stinging
- Baseline evaporimetry measurements without contact lenses
- Non-invasive pre-ocular tear film break up time (Tearscope)
- Lipid layer thickness (Tearscope)
- Lipid layer thickness (LipiView II)
- Evaporimetry measurements will be repeated at least 15 minutes after the initial baseline measurement.
- Non-invasive pre-ocular tear film break up time (Tearscope)
- Lipid layer thickness (Tearscope)
- Lipid layer thickness (LipiView II)
- The participant will wipe away petroleum jelly from skin surrounding the ocular surface using a tissue.
- Contact lenses will be given to the participants in a masked manner (Section 4.3.7).
- The study contact lenses will be inserted by the participant.
- The lenses will be allowed to settle for at least 15 minutes.
- The participant will apply a thin layer of petroleum jelly will be applied to the skin surrounding the eye using a cotton tipped applicator to minimize the amount of evaporation from the skin.
- The participant will be asked to give subjective monocular ratings for:
 - Comfort
 - Dryness
 - Burning or stinging
- Baseline evaporimetry measurements with contact lenses.
- Non-invasive pre-lens tear film break up time (Tearscope)
- Lipid layer thickness (Tearscope)
- Lipid layer thickness (LipiView II)

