4.5 STUDY PROCEDURES

Table 3 summarizes the visits and procedures for the study.

Table 3: Summary of procedures to be conducted at scheduled visits

| Procedure | Visit 1 | Visit 2 | Visit 3 | Instrument/application |
|----------------------------------------------|---------|---------|---------|--------------------------------------|
| Informed consent (screening) | √ | | | Investigator |
| Demographics | √ | | | Investigator |
| Contact lens history | √ | | | Investigator |
| Medical history | √ | √ | √ | Investigator |
| CLDEQ-8 | √ | | | Questionnaire (paper) |
| VA with spectacles or refraction | √ | √ | √ | Visual acuity chart |
| Meibomian gland assessment | √ | | | Meibomian Gland Evaluator (overhead) |
| LD margin assessment | √ | | | Stamp |
| Stamp biomicroscopy (with staining) | √ | | √ | Stamp |
| Confirmation of inclusion/exclusion criteria | √ | | | Investigator |
| Training of study nurses | √ | | | Investigator |
| VA with contact lenses | √ | √ | √ | Visual acuity chart |

| Procedure | Visit 1 | Visit 2 | Visit 3 | Instrument/application |
|------------------------------------------------------------|---------|---------|---------|------------------------------------------|
| Over-refraction | √ | | | Phoropter |
| Lens fit assessment | √ | √ | √ | S t amp |
| Anterior eye photography | √ | | | S t amp and camera |
| Evaporimetry practice | √ | | | Evaporimeter |
| Removal of contact lenses | √ | | √ | Participant |
| Measurement of volume inside the goggle | √ | | | Modified swimming goggle |
| S t amp biomicroscopy (safety with staining) | √ | | | S t amp |
| S t amp biomicroscopy (white light) | | √ | | S t amp |
| Subjective assessment (comfort, dryness, burning/stinging) | | √ | √ | Questionnaire (paper) |
| Application of petroleum jelly | | √ | √ | Participant |
| Evaporimetry | | √ | √ | Prototype evaporimeter |
| Non-invasive breakup time | | √ | √ | Keeler Tearscope |
| Lp d layer thickness | | √ | √ | Keeler Tearscope, TearScience Lp View II |
| Removal of petroleum jelly | | √ | √ | Participant |
| Study completion and exit | | | √ | N/A |

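### The introduction says the study will validate the prototype evaporimeter, but no reference device is used and no agreement or repeatability analysis is planned; the data already collected can support a within-visit repeatability claim only.

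*Combined protocol and SAP*

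**What the plan says.** The validation aim appears once, at the end of section 1: "The study will also serve to validate the novel, in-house developed evaporimeter". Section 2 does not carry it forward. It begins "The objective of the study is to compare the rate of tear evaporation, measured with a novel evaporimeter, before and after" and concerns lens wear in symptomatic and asymptomatic wearers. Validation is also absent from the hypotheses (section 3), the sample size section (4.2.1) and the statistical section (10.1).

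Section 1 describes one commercial device, the Eye-VapoMeter, which "was validated for ocular use in 2014". Table 3 (section 4.5) lists only the "Prototype evaporimeter" for evaporimetry at Visits 2 and 3.

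Two layers of replication are built in. At Visit 2, before any lens is inserted, section 4.4.3 says "Evaporimetry measurements will be repeated at least 15 minutes after the initial baseline measurement". Within a session, section 4.5.16 says "Three consecutive measurements of open eye and closed eye measurements will be taken", and then "The average of three ocular surface evaporation rates will be calculated for each eye". The plan does not say how the second no-lens session will be used.

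Section 10.1 says "Table 4 lists the primary outcome variables and anticipated statistical procedures". The table gives the slope, a repeated-measures ANOVA with post hoc tests and a paired t-test for the effect of lens type, and Pearson and Spearman correlations with subjective ratings, break-up time, lipid layer thickness, ocular surface area and goggle volume.

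**The concern.** To validate a measuring device one normally shows how close it comes to a reference, how well it repeats itself, or both. The plan collects nothing that bears on the first and analyses nothing that bears on the second. Table 4 has no within-participant SD, coefficient of repeatability, intraclass correlation (ICC), limits of agreement or acceptance criterion.

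This matters because the slope from this prototype is the primary outcome. If the final report repeats the sentence in section 1, it will claim something that the planned analyses cannot back. The plan would also leave the size of the device's measurement error unreported, although participants sit through a repeat session that could supply it. Later users of the instrument would need that figure.

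**Working it through.** The documents give no agreement limit, repeatability target or variance, so there is no stated figure to reproduce. The check has two parts.

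**1. What each planned element can show about the device**

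| Element | Agreement with a reference | Repeatability | Construct validity |
|---|---|---|---|
| Prototype as the only evaporimeter (Table 3) | Not estimable at any sample size | – | – |
| Repeated-measures ANOVA and paired t-test (Table 4) | No | No; could at most detect a mean shift if both baselines were entered as levels | Weak (lens against no lens) |
| Symptomatic against asymptomatic (section 3) | No | No | Weak (known groups) |
| Correlations (Table 4) | No | No | Weak (convergent) |
| Two no-lens sessions (4.4.3) | No | Yes, but no analysis planned | – |
| Triplicate readings (4.5.16) | No | Yes, within session, but only averaged | – |

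**2. What the existing repeat data would deliver**

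Inputs: at least 20 completers (10 symptomatic and 10 asymptomatic) and at most 50 randomized (section 4.2.2); two no-lens sessions (section 4.4.3). I take one value per participant per session, because both eyes are measured in a single goggle placement (section 4.5.16). The value is the session mean of three readings, so Sw below is the SD of such means.

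*Within-participant SD.* With d the difference between a participant's two sessions, Sw² = Σd²/(2n) on n degrees of freedom. The 95% interval multiplies the estimate by √(df/χ²).
- n = 20: √(20/34.170) = 0.765 and √(20/9.591) = 1.444.
- n = 50: √(50/71.420) = 0.837 and √(50/32.357) = 1.243.

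If the mean shift between sessions is removed first, one degree of freedom is lost. With 19 df the factors are √(19/32.852) = 0.760 and √(19/8.907) = 1.461, which is almost the same.

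*Coefficient of repeatability.* 1.96 × √2 × Sw = 2.77 × Sw.

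*Limits of agreement between sessions.* Each limit has a 95% margin of about 1.96 × √(3/n) SDs of the differences: 0.76 at n = 20 and 0.48 at n = 50.

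*ICC.* An observed value has to be assumed. For a one-way ICC with two sessions, F = (1 + ICC)/(1 − ICC), and each bound is (F* − 1)/(F* + 1), where F* is F divided or multiplied by the relevant 97.5% F quantile.

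| Assumed observed ICC | 95% CI, n = 20 | 95% CI, n = 50 |
|---|---|---|
| 0.7 | 0.39 to 0.87 | 0.53 to 0.82 |
| 0.8 | 0.57 to 0.92 | 0.67 to 0.88 |
| 0.9 | 0.77 to 0.96 | 0.83 to 0.94 |

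A repeatability estimate is therefore feasible from data already planned, but imprecise with 20 participants.

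Two features of the plan limit its meaning. In section 4.4.3, break-up time, Tearscope and LipiView tests come between the two sessions, so the difference includes any effect of those tests. In section 10.1, the slope window is to be chosen from the first 20 completers, so repeatability computed in the same 20 may look too good.

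**The case against.** The best defence is that validation is a side remark. The stated purpose of the pilot is to compare two lenses, and no objective, endpoint, sample size or decision depends on the validation sentence. That is right, and it limits the seriousness of the point. It is also a reason to correct the sentence.

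Second, validation need not mean agreement or repeatability. Section 3 predicts higher evaporation with lenses than without, and in symptomatic than in asymptomatic wearers, and Table 4 correlates evaporation with other tear film measures. A reader might infer that the study can say nothing at all about validity. The documents do not support that: these results would be weak known-groups and convergent evidence. But the plan does not present them as validation or set a criterion, and none of them measures the device's error or bias.

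Third, section 1 itself reports a lack of reliable commercial evaporimeters and says the prototype was built to overcome problems with the Eye-VapoMeter. That device is therefore not offered as a gold standard. A comparison was possible, but its absence is not an error in the lens study.

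Fourth, section 10.1 calls its procedures anticipated and allows additional analysis. That leaves room for a repeatability analysis without specifying one. Nor is the spread of the triplicates lost: section 4.5.16 saves the raw recordings, so it is only unreported.

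**Conclusion.** The point holds in a limited form. As written, the plan cannot support a claim that the evaporimeter was validated: agreement with a reference cannot be estimated at any sample size, and repeatability could be estimated but is not planned. The repeat no-lens sessions would fix Sw to within about 0.77 to 1.44 times its estimate with 20 participants, or 0.84 to 1.24 times with 50. This assumes one value per participant per session, roughly normal differences and no large shift between sessions.

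Three stronger readings should be resisted.
- Counting both eyes as independent would make the interval look narrower, but the eyes are measured together in one person.
- A reader might infer that a null lens result could not be told apart from a noisy device. The confidence interval of the paired lens difference already contains measurement error and answers that question.
- Setting the mean difference between the lenses against 2.77 × Sw would compare a group mean with a limit for individuals. Sw also comes from the same eye without a lens, while the lens contrast is between eyes with lenses in.

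The lens comparison can go ahead. What needs to change is the claim and one analysis, and in a pilot this is a modest recommendation.

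**What to change.** 1. In section 1, replace *validate* with *assess the within-visit repeatability of*. If the stronger word is to stay, a reference measurement has to be added.
2. Add a row to Table 4 comparing the two no-lens Visit 2 sessions, with eyes nested in participant: mean difference, 95% limits of agreement, Sw, coefficient of repeatability (2.77 × Sw), and ICC with its confidence interval. Add the within-session SD of the triplicate readings.
3. State beside it that the Tearscope and LipiView tests fall between the sessions, so the difference includes any effect of them. State also that the slope window is chosen on the first 20 completers, so repeatability in them may look too good. Report later participants separately if there are any.
4. For the lens comparison, report the confidence interval of the paired DAILIES TOTAL1 minus Biotrue ONEday difference.

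I would not average the two no-lens sessions into a single baseline on the strength of this point. That would alter the main comparison and pool readings taken before and after the intervening tests.

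Unless a reference device is added, the cost is a wording change and a small analysis of data already collected, with no new visits or measurements. The downside is a weaker claim: same-visit repeatability, not agreement with a reference or between-day reproducibility.
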